### 5.1.3 Statistical Methods for Observational Objectives

No hypotheses will be tested. Descriptive statistics will be presented by group and by pooled group for subjects included in South Korea and Thailand (Groups 1 & 10 pooled, Groups 2 & 11 pooled, and Groups 3 & 12 pooled).

#### 5.1.3.1 Statistical Methods

##### *Immunogenicity*

The immunogenicity descriptive analyses will include the following:

Ab titers against meningococcal serogroups A, C, Y, and W measured by rSBA (in 50 subjects per group in Groups 2, 5, and 8; and in 100 subjects per group in Groups 1, 4, and 7) before and 30 days after vaccination with MenACYW conjugate vaccine:

- GMT and 95% CI
- Titer distribution and RCDCs
- Percentage of subjects with titer  $\geq 1:8$  and  $\geq 1:128$  and 95% CI
- Percentage of subjects with titer  $\geq 4$ -fold rise from pre-vaccination to post-vaccination, and 95% CI
- Percentage of subjects with rSBA vaccine seroresponse defined as follow:
  - For a subject with a pre-vaccination titer  $< 1:8$ , the post-vaccination titer must be  $\geq 1:32$
  - For a subject with a pre-vaccination titer  $\geq 1:8$ , the post-vaccination titer must be at least 4-fold greater than the pre-vaccination titer

##### *Safety*

For this trial, the safety data will be assessed by applying descriptive statistical methods, supplemented by the calculation of CIs to aid interpretation. The exact binomial distribution (Clopper-Pearson method) for proportions will be used in the calculation of the 95% CIs of events. Analysis tables and listings will contain at least the descriptions listed in Table 5.2

Table 5.2: Statistical analyses for safety observational objectives

Safety Events	Time and Group	Description
Immediate unsolicited systemic AE	Within 30 minutes after injection for all subjects in Groups 1 to 12 at D0	Proportion of subjects that have the event, MedDRA terms, intensity, relationship to vaccine, study discontinuation
Solicited injection site reactions	Up to 7 days after D0 for all subjects in Groups 1 to 12	Proportion of subjects that have the event, onset, duration, intensity, action taken, study discontinuation, temperature collection routes
Solicited systemic reactions	Up to 7 days after D0 for all subjects in Groups 1 to 12	Proportion of subjects that have the event, onset, duration, intensity, action taken, study discontinuation
Unsolicited AE	Up to 30 days after D0 for all subjects in Groups 1 to 12	Proportion of subjects that have the event, MedDRA terms, onset, duration, intensity, relationship, action taken, study discontinuation
SAE	From Visit 1 to Visit 2 for all subjects in Groups 1 to 12	Proportion of subjects that have the event, MedDRA terms, onset, duration, relationship, seriousness criteria, outcome, study discontinuation

### 5.1.4 Complementary Outputs

Additional analyses by gender will be provided in Appendix 15 of the CSR.

Immunogenicity analyses:

- hSBA GMTs and 95% CI at each time point – Per-Protocol Analysis Set
- Percentage of subjects with hSBA titers  $\geq 1:4$  and  $\geq 1:8$  and 95% CI – Per-Protocol Analysis Set
- rSBA GMTs and 95% CI at each time point – Per-Protocol Analysis Set
- Percentage of subjects with rSBA titers  $\geq 1:8$  and  $\geq 1:128$  and 95% CI – Per-Protocol Analysis Set

Safety analyses:

Safety overview after vaccine injection –Safety Analysis Set

## 5.2 Analysis Sets

Three analysis sets will be used: the Full Analysis Set (FAS), the Per-Protocol Analysis Set (PPAS), and the Safety Analysis Set (SafAS).

### **5.2.1 Full Analysis Set**

The FAS is defined as the subset of subjects who received at least one dose of the study vaccine(s) and had a valid post-vaccination blood sample result. All subjects will be analyzed according to the treatment group to which they were randomized.

### **5.2.2 Per-Protocol Analysis Set**

The PPAS is a subset of the FAS. The subjects presenting with at least one of the following relevant protocol deviations will be excluded from the PPAS:

- Subject did not meet all protocol-specified inclusion criteria or met at least one of the protocol-specified exclusion criteria
- Subject did not receive vaccine
- Subject received a vaccine other than the one that he / she was randomized to receive
- Preparation and / or administration of vaccine was not done as per-protocol
- Subject did not provide the post-dose serology sample at Visit 2 in the proper time window or a post-dose serology sample was not drawn
- Subject received a protocol-prohibited therapy / medication / vaccine
- Subject's serology sample at Visit 2 did not produce a valid test result
- Subject had other protocol violation that affected the subject's immune response, as determined by the clinical team prior to locking the database

### **5.2.3 Safety Analysis Set**

The SafAS is defined as those subjects who have received at least one dose of the study vaccine(s) and have any safety data available. All subjects will have their safety analyzed according to the vaccine(s) they actually received. If the vaccine(s) received by a subject does not correspond to any study group, the subject will be excluded from the SafAS. The corresponding safety data will be presented in separate listings.

### **5.2.4 Populations Used in Analyses**

All immunogenicity analyses will be performed on the PPAS. Additional immunogenicity analyses will be performed for exploratory purposes on the FAS. In the FAS, subjects will be analyzed by the vaccine group to which they were randomized.

All safety analyses will be performed on the SafAS. Subjects will be analyzed according to the vaccine(s) they actually received.

## 5.3 Handling of Missing Data and Outliers

### 5.3.1 Safety

No replacement will be done. In subject listings, partial and missing data will be clearly indicated as missing.

#### 5.3.1.1 Immediate

For unsolicited non-serious systemic AEs, a missing response to the “Immediate” field is assumed to have occurred after the 30-minute surveillance period and will not be imputed.

For SAEs, missing or partially missing elapsed time from last vaccination recorded if within 24 hours will remain missing and not be imputed. Such SAEs will not be considered as immediate.

#### 5.3.1.2 Causality

Missing causality (relationship) for unsolicited non-serious AEs and SAEs will be considered at the time of analysis as related to vaccination.

#### 5.3.1.3 Measurements

Partially missing temperatures will be handled as described in [Section 4.4.1.1.1](#)

#### 5.3.1.4 Intensity

For solicited reactions, missing intensities will be handled as described in [Section 4.4.1.1.1](#). For unsolicited non-serious AEs, missing intensities will remain missing and will not be imputed.

#### 5.3.1.5 Start Date and Stop Date

Missing or partially missing start dates for unsolicited AEs will remain missing and not be imputed. If either the start or stop date is missing or partially missing, the time of onset will be considered to be missing. Nevertheless unsolicited AEs with missing time of onset will be included in analyses according to the visit collected.

Missing or partially missing stop dates for AEs (solicited reactions and unsolicited AEs) will remain missing and not be imputed.

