### 9.3.2.2 Safety Endpoints

The observational endpoints for the evaluation of safety are:

- Occurrence, nature (Medical Dictionary for Regulatory Activities [MedDRA] preferred term), duration, intensity, and relationship to vaccination(s) of any unsolicited systemic AEs reported in the 30 minutes after vaccination(s).
- Occurrence, time to onset, number of days of occurrence, intensity, action taken, and whether the reaction led to early termination from the study, of solicited (prelisted in the subject's diary card and CRF) injection site reactions occurring up to 7 days after vaccination(s).
- Occurrence, time to onset, number of days of occurrence, intensity, action taken, and whether the reaction led to early termination from the study, of solicited (prelisted in the subject's diary card and CRF) systemic reactions occurring up to 7 days after vaccination(s).
- Occurrence, nature (MedDRA preferred term), time to onset, duration, intensity, action taken, relationship to vaccination (for systemic AEs only), and whether the event led to early termination from the study, of unsolicited AEs up to Visit 2 after vaccination(s).
- Occurrence, nature (MedDRA preferred term), time to onset, duration, seriousness criteria, relationship to vaccination, outcome, and whether the SAE led to early termination from the study, of SAEs throughout the trial.

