#### 4.4.1.2.4 Time of Onset

Time of onset is derived from the start date of the unsolicited non-serious AE provided in the clinical database and the date of last vaccination:

- start date of the unsolicited non-serious AE – date of previous vaccination

The time of onset should be considered as missing only if one or both of the dates are missing or partially missing.

The unsolicited non-serious AEs will be analyzed “Within 30 days”, which corresponds to AEs with a time of onset between 0 and 30 days after vaccination or missing. An AE with missing time of onset will be considered to have occurred just after the vaccination indicated by the visit number, so will be included in these tables.

Note: Unsolicited non-serious AE that occurred before vaccination (negative time of onset) or with a time of onset higher than defined above will not be included in analysis, but will be listed separately.

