#### 4.4.1.2.5 Duration

Duration is derived from the start and stop dates of the unsolicited non-serious AE provided in the clinical database:

- stop date of unsolicited non-serious AE - start date of unsolicited non-serious AE + 1.

The duration should be considered as missing only if one or both of the start and stop dates of the unsolicited non-serious AE is missing or partially missing.

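### SAP 5.3.1.5 makes time of onset missing when only the stop date is missing; this contradicts SAP 4.4.1.2.4 and would move ongoing adverse events starting on Day 31-44 into the 30-day tables

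*SAP*

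**What the plan says.** **Derivation rule.** SAP 4.4.1.2.4 defines time of onset as the AE start date minus the date of the previous vaccination. On missing values it says: "The time of onset should be considered as missing only if one or both of the dates are missing or partially missing". The dates meant are the two in the formula; the stop date is not one of them.

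**Missing-data rule.** SAP 5.3.1.5 says: "If either the start or stop date is missing or partially missing, the time of onset will be considered to be missing". It adds: "Nevertheless unsolicited AEs with missing time of onset will be included in analyses according to the visit collected". Missing stop dates are not imputed.

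**Placement rule.** SAP 4.4.1.2.4 analyses unsolicited non-serious AEs within 30 days, meaning onset from 0 to 30 days or missing. On the missing case: "An AE with missing time of onset will be considered to have occurred just after the vaccination indicated by the visit number". Its note covers AEs that began before vaccination "or with a time of onset higher than defined above will not be included in analysis, but will be listed separately".

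**Duration.** SAP 4.4.1.2.5 has the start-and-stop condition for a different variable. Its sentence opens "The duration should be considered as missing only if one or both of the start and stop dates of the unsolicited non-serious AE" and closes by naming absent or incomplete dates as the trigger.

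**Where onset is used.** The protocol's unsolicited-AE endpoint (9.3.2.2) lists "Occurrence, nature (MedDRA preferred term), time to onset, duration, intensity, action taken, relationship to vaccination (for systemic AEs only"), and the unsolicited-AE row of SAP Table 5.2 plans "Proportion of subjects that have the event, MedDRA terms, onset, duration, intensity, relationship, action taken, study discontinuation".

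**Data collection.** Unsolicited AEs are collected from Day 0 to Visit 2, which falls 30 to 44 days after vaccination (SAP 3.1). Under footnote a of protocol 9.3.2.3.3, an AE for which no stop date is obtained counts as ongoing at the end of the trial.

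**The concern.** A stop date carries no information about when an event began. Under 5.3.1.5, an AE with a fully known start loses its onset because it had not resolved, or because its stop date was incomplete. The start-or-stop condition is the right one for duration, so it seems to have been attached to the wrong variable. That is an inference, but 4.4.1.2.5 supports it closely. SAP 5.7, which lists changes to the planned analyses, does not mention the point.

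Two things are at stake if the sentence is programmed as written:

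- Time to onset, a protocol safety endpoint and a planned output, is lost for every unsolicited AE without a complete stop date.
- Missing onset works as a ticket into the 30-day tables, so for AEs starting after Day 30 inclusion depends on whether the event resolved and not on when it started.

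**Working it through.** The plan gives no figure to reproduce here. The check traces both rules as written.

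**Inputs**
- Onset rule A: SAP 4.4.1.2.4 (start date and vaccination date).
- Onset rule B: SAP 5.3.1.5 (start date and stop date).
- Inclusion: onset 0-30 or missing is tabulated; onset above 30 is listed separately (SAP 4.4.1.2.4).
- Collection: Day 0 to Visit 2, with Visit 2 on Day 30-44 (SAP 3.1).
- Assumptions: the start and vaccination dates are complete, the AE is attributed to the single vaccination at Visit 1, and an ongoing AE has no complete stop date in the database.

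**Rule trace**

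| AE start | Stop date | Rule A (4.4.1.2.4) | Rule B (5.3.1.5) |
|---|---|---|---|
| Day 5 | complete | onset 5, tabulated | onset 5, tabulated |
| Day 5 | none | onset 5, tabulated | onset missing, tabulated |
| Day 30 | none | onset 30, tabulated | onset missing, tabulated |
| Day 31 | none | onset 31, listed separately | onset missing, tabulated |
| Day 37 | complete | onset 37, listed separately | onset 37, listed separately |
| Day 37 | none | onset 37, listed separately | onset missing, tabulated |
| Day 44 | none | onset 44, listed separately | onset missing, tabulated |

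Over every start day from 0 to 44:
- With a complete stop date, the rules agree on all 45 days.
- Without one, the onset value differs on all 45 days, and table inclusion differs on exactly 14 days (Day 31 to Day 44).

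**Share of start days misplaced for an ongoing AE.** With Visit 2 on Day V there are V + 1 possible start days (Day 0 to Day V), of which V − 30 lie beyond Day 30. The share is (V − 30)/(V + 1):
- V = 30: 0/31 = 0%
- V = 33: 3/34 = 8.8%
- V = 37: 7/38 = 18.4%
- V = 44: 14/45 = 31.1%

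These are shares of calendar days. They do not estimate the share of AEs or of subjects.

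**Does the visit-based wording in 5.3.1.5 prevent this?** No. SAP 4.4.1.2.3 uses the visit number only to identify the last vaccination, and there is one vaccination visit, so every such AE is assigned to it.

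**The case against.** The strongest reply is that this is a wording slip and the operative rule is already in the SAP. Section 4.4.1.2.4 is the derivation section, its formula contains no stop date, and it states its condition exclusively. A programmer working from it would never consult the stop date. That is a fair account of how the sentence probably arose, and harm follows only if 5.3.1.5 is applied. But 5.3.1.5 is the section that governs missing dates, it is explicit, and nothing ranks the two. Two programmers could each follow the SAP and produce different safety tables.

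Other points have some force:

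- **Two sections combined.** The Day 31-44 effect takes the missing value from 5.3.1.5 and the window from 4.4.1.2.4. That is so, but 4.4.1.2.4 is the only place the SAP says what happens in the tables to an AE with missing onset.
- **Endpoint scope.** The protocol endpoint covers unsolicited AEs up to Visit 2, so a Day 38 event is misplaced only relative to the SAP's 30-day window. This stands as context. It does not justify tabulating ongoing late events and listing resolved ones.
- **Diary wording.** Protocol 9.3.2.3.3 has a Day 0 to Day 30 heading and asks parents to record events over 30 days, so later events may be captured less completely. They can still be in the database, because the endpoint, the procedures tables and SAP 3.1 all run to Visit 2.
- **Ongoing taken as missing stop date.** The SAP does not say so in terms. Given the protocol footnote and the absence of imputation, it is the natural reading.
- **Size.** A misplaced AE needs Visit 2 after Day 30, a start after Day 30 and no complete stop date. It alters a subject-level proportion only if that subject has no other qualifying event. The number is probably small.

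**Conclusion.** The contradiction is real, and 5.3.1.5 is wrong as written. If followed, it removes a known onset from every unsolicited AE with a complete start date and no complete stop date. It also places such AEs starting on Day 31-44 in the 30-day tables, while resolved AEs with the same start days are listed separately.

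The number of events affected cannot be obtained from the documents. The calendar bounds above apply to ongoing AEs only and rest on the assumptions stated there.

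The consequences are limited. Ongoing AEs starting on Day 0-30 are still counted and lose only their onset. Stop dates of related AEs are actively sought (protocol 9.3.2.3.3, footnote a), so missing ones should fall mainly on unrelated AEs. Safety is descriptive, and no primary or secondary immunogenicity result changes.

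SAP 4.4.1.3.2 sends serious AEs (SAEs) to the onset method in 4.4.1.2.4, so they are affected only if 5.3.1.5 is read to cover them. The correction should be made before the safety tables are programmed, because two defensible readings of the SAP give different output.

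**What to change.** In SAP 5.3.1.5, replace the sentence with one that separates the two variables: time of onset is missing when the AE start date or the vaccination date is missing or incomplete; duration is missing when the AE start date or stop date is missing or incomplete. The next sentence, on keeping AEs with missing onset in the analysis, can stay.

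Add a short confirmation that SAE onset follows 4.4.1.2.4, as 4.4.1.3.2 already indicates.

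The cost is one sentence and that confirmation. No new data and no new derivation are needed, since 4.4.1.2.4 and 4.4.1.2.5 already hold both rules. All AEs with a known start after Day 30 would then go to the separate listing, whether resolved or ongoing.

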#### 5.3.1.6 Action Taken

Missing actions taken will remain missing and not be imputed.

### 5.3.2 Immunogenicity

Missing data will not be imputed. No test or search for outliers will be performed.

In order to appropriately manage extreme values (undetectable responses  $< \text{LLOQ}$  and  $\geq [\text{ULOQ}]$ ), the following computational rule is applied to the values provided in the clinical database for each BL drawn for analysis purposes:

- If a value is < LLOQ, then use the computed value LLOQ/2
- If a value is between  $\geq$  LLOQ and < ULOQ, then use the value
- If a value is  $\geq$  ULOQ, then use the computed value ULOQ

#### 5.4 Interim / Preliminary Analysis

No interim / preliminary analyses are planned.

#### 5.5 Determination of Sample Size and Power Calculation

[REDACTED]

#### 5.6 Data Review for Statistical Purposes

A review of the data has been anticipated through the data review process led by data management before database lock. This review of the data included a statistical review.

#### 5.7 Changes in the Conduct of the Trial or Planned Analyses

The SAP core V1.0 was updated to version 2.0 to reflect the changes following amendment 3 of the protocol (version 4.0 dated 11Sep2017; inclusion of study groups in Thailand).

Moreover, for MMRV antigens and in order to reflect the assay used for analysis, the respective thresholds to be considered as clinical endpoint were changed as below:

- anti-measles Ab concentrations  $\geq$  255 mIU/mL
- anti-mumps Ab concentrations  $\geq$  10 Mumps Ab units/mL
- anti-rubella Ab concentrations  $\geq$  10 IU/mL
- anti-rubella Ab concentrations  $\geq$  5 gpELISA Ab units/mL

Definition of vaccine response for PT and FHA antigens was modified as follow:

- If the pre-vaccination concentration is  $\geq$  4 x LLOQ, then the post-vaccination concentration is  $\geq$  2 x the pre-vaccination concentration

- If the pre-vaccination concentration is  $< 4 \times \text{LLOQ}$ , then the post-vaccination concentration is  $\geq 4 \times$  the pre-vaccination concentration

